- A weak electrical current is applied to the brain via the scalp during tDCS using two surface electrodes. Current evidence shows that tDCS applied to motor and non-motor areas according to the present tDCS safety guidelines produces only minor adverse effects in healthy humans and patients with varying neurological disorders. One published safety study of tDCS, using stimulation parameters similar to this study, evaluated 103 subjects²⁵, and found no adverse effects on cognitive and psychomotor measures, nor EEG changes during or after 20 min of treatment. In a double-blind, sham-controlled study³⁹ it has been shown that comparing tDCS and sham stimulation of the motor cortex elicited minimal discomfort and difference in the duration of tingling sensations. Another study summarized adverse effects of 567 tDCS sessions over motor and non-motor cortical areas (occipital, temporal, parietal) in 102 subjects who participated in tDCS studies⁴⁰.
 - **active** tDCS intervention causes a sensation of mild tingling and itching under the electrodes that lasts for 10 to 30 seconds. Less frequently, a burning sensation or a burn is reported. Headache, visual sensations, difficulty concentrating, nervousness or overexcitability during procedure, unpleasant sensations, dizziness, fatigue, insomnia, and nausea are infrequently reported after tDCS. Because 10-20 conductive paste is

added to the electrodes to deliver tDCS, subjects will get paste in their hair.

- Risk will be minimized by the following steps:
 - First subjects are fully informed of all risks during the informed consent process.
 - For tDCS we use stimulation parameters that are well below the maximum levels that are considered safe. We will ensure there is no skin breakdown or lesions in the vicinity of electrode placement. The electrodes have connectors on their back to eliminate the possibility of contact with scalp which could cause a burn. We monitor electrode impedances during stimulation to ensure good conductance of current to scalp.
 - For TMS, we use stimulation procedures that fall within the guidelines recommended at the conclusion of the NIH Panel on TMS (see Wasserman ⁴¹). Patients will be fully informed of the possibility of seizure, the plan for care in event of a seizure, and any foreseeable financial or medical consequences resulting from a seizure.
 - All subjects will wear ear plugs during testing sessions. TMS will be stopped if an ear plug falls out during a session.

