The PIs and study physician would provide documentation that the seizure happened during a TMS session, that it does not constitute epilepsy, and that seizures caused by TMS have not resulted in future seizures. Seizures induced during electroconvulsive therapy (ECT) for depression, for example, do not cause driving privileges to be revoked in the state of Arkansas. Like ECT, a seizure occurring after TMS would not cause driving privileges to be revoked.

Benefits

Potential benefits to subjects participating in the study include the following:

- The potential benefits to participants include personal satisfaction knowing

Version 10 Revised 11/21/2014

they have helped further research that could benefit patients with stroke and education about research studies.

- Further stroke patients could benefit from the treatment intervention in terms of increase ambulation and social well-being.
- Participants are not guaranteed a benefit from this study.

Data Safety and Monitoring

Data safety and monitoring will be performed in two ways. First, independent study monitoring will be performed by the Research Support Center at UAMS after the first 1-2 participants are enrolled. Thereafter, independent study monitoring will be performed by the Research Support Center at UAMS. Monitoring would occur according to the RSC monitoring plan. The Data and Safety Monitoring Plan describes operating procedures that will be in place to monitor compliance, study data validity and integrity, participant safety, individuals and/or entities (e.g., IRB) that will be involved in monitoring these procedures, and the frequency/regularity of this monitoring.

Adverse Events

Eliciting and Reporting Adverse Events:

Subjects will be monitored for the occurrence of adverse events throughout the study procedures.

Adverse Events Reporting and Evaluation:

All adverse events occurring during the course of the clinical study, whether device-related or otherwise, will be recorded on the Adverse Event CRF. For all adverse events, the study physician will provide an assessment of the adverse event, its treatment and resolution, and its relationship to the investigational device. All adverse events will be reported to the Sponsor and/or IRB in accordance with applicable institutional and federal regulatory guidelines.

Identification of Adverse Events:

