An adverse event is defined as any new medical problem, or exacerbation of an existing problem, experienced by a subject while enrolled in the study, whether or not it is considered device-related.

Relationship of Adverse Events to the Study Device:

The study physician will assess the relationship of the adverse event to the investigational device. The relationship will be assessed using the following categories:

- Definitely Related: A direct cause and effect relationship between the investigational device and the adverse event exists.

- Possibly Related: A direct cause and effect relationship between the investigational device and the adverse event has not been clearly demonstrated, but is likely or very likely.
- Unlikely Related: A direct cause and effect relationship between the investigational device and the adverse event is improbable, but not impossible.
- Unrelated: The adverse event is definitely not associated with the investigational device.

Unanticipated Adverse Device Effects:

An unanticipated adverse device effect is defined as “any serious adverse effect on health or safety, or any life-threatening problem, or death caused by, or associated with, a device; if that effect, problem, or death was not previously identified in nature, severity, or degree of incidence in the investigational plan, or application (including supplementary application), or any other unanticipated serious problem associated with a device that relates to the rights, safety, or welfare of subjects.”

In the event unanticipated adverse effect occurs, the investigator will report the event(s) according to federal and institutional policies.

Serious Adverse Events:

Each adverse event will be assessed for its seriousness using the criteria outlined below. The term serious adverse event is not synonymous with a “severe” adverse event, which may be used to describe the intensity of an event experienced by the subject. An adverse event will be classified as serious if it meets any of the following criteria:

- Results in, or contributes to, a death
- Life-threatening (i.e., the subject was, in the opinion of the investigator, at risk of death at the time of the event, but it does not include an event that, had it occurred in a more severe form, might have caused death)
- Results in permanent disability or incapacity (i.e., permanent impairment of a body function or permanent damage to a body structure)
- Requires in-subject hospitalization or prolongs hospitalization

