- Necessitates medical or surgical intervention to preclude a permanent disability or incapacity
- Results in a congenital anomaly or birth defect

Non-serious adverse events are all events that do not meet the criteria for a “serious” adverse event.

Severity:

Each adverse event will be assessed for its severity, or the intensity of an event experienced by the subject, using the following.

- Mild: Discomfort noticed, but no disruption to daily activity.
- Moderate: Discomfort sufficient to reduce or affect normal daily activity.
- Severe: Inability to work or perform normal daily activity.

Anticipated Adverse Events and Pre-existing conditions:

Pre-existing conditions will not be reported as an adverse event unless there has been a substantial increase in the severity or frequency of the problem which has not been attributed to natural history.

Data Handling and Recordkeeping

Each subject's name, birth date, address and phone number will be obtained for purposes of follow-up. We will ask for each subject's drug use history, medical history, and current drug use. Experimental data and questionnaire data will be collected. This information will be coded into the Microsoft Excel. Each subject's personal information will be de-identified in the database by using codes comprising the subject number and date and time the subject was tested. The PIs and study personnel at UAMS and UCA will have access to subject identities in order to arrange follow-up and to call them as part of the research project, such as follow-up contact. If subjects prefer e-mail correspondence research personnel will send e-mails for scheduling, follow-up, and research-related communication.

Data Analysis

Aims 1-3. Difference scores from baseline will be calculated for each outcome measure. A mixed model ANOVA with group (active tDCS groups versus sham tDCS) as the between subjects factor and time of assessment (pre, weeks 1-4, & one week and one month post) as the within subjects factor will be used to test all aims. A significant group effect, with active tDCS > sham tDCS, for any of the outcome measures would indicate that anodal tDCS augments gait training. A significant main effect of time would be evaluated using planned contrasts where we expect post treatment assessments to be improved relative to baseline. Interim analyses will be completed at critical stages during the protocol.

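### The pre-existing-condition rule keeps some worsening from being reported as an adverse event, which contradicts the protocol's own definition and applies a causal judgement before the relationship rating

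*Combined protocol and SAP*

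**What the plan says.** All the relevant text is in the combined protocol and SAP.

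- **Definition** (Identification of Adverse Events). An adverse event is "any new medical problem, or exacerbation of an existing problem, experienced by a subject while enrolled in the study", and it counts as one "whether or not it is considered device-related". There is no size threshold and no condition on cause.
- **Recording** (Adverse Events Reporting and Evaluation). The rule is that "All adverse events occurring during the course of the clinical study, whether device-related or otherwise, will be recorded on the Adverse Event CRF". The study physician then assesses each adverse event, its treatment and resolution, and its relationship to the device.
- **Reporting** (same section). "All adverse events will be reported to the Sponsor and/or IRB in accordance with applicable institutional and federal regulatory guidelines".
- **Pre-existing conditions** (Anticipated Adverse Events and Pre-existing conditions). The sentence opens with "Pre-existing conditions will not be reported as an adverse event" and then gives its only exception: "unless there has been a substantial increase in the severity or frequency of the problem which has not been attributed to natural history".

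The last rule sets two conditions, and both must be met. The protocol does not define what counts as substantial. It does not say who attributes a worsening to natural history, by what criteria, or whether that person is blinded to arm.

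**The concern.** Whether a worsening reflects the natural course of a condition is a question of cause. The protocol already has a place for that question: the study physician's four-category relationship rating, made after an event has been classed as an adverse event. The pre-existing-condition sentence asks it earlier, as a condition of entry, and adds an undefined threshold of size.

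The complaints most exposed are ones the trial has reason to watch. Device Risks lists headache among the effects seen after tDCS and adds that "dizziness, fatigue, insomnia, and nausea are infrequently reported after tDCS". Stroke survivors may already have any of these at enrolment. If a mild existing headache becomes somewhat more frequent during the four treatment weeks, one clinician may see background variation and another a stimulation effect. A sham-controlled trial can inform that question only if such changes are captured the same way in every participant, whatever the first impression of their cause.

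**Working it through.** No figure in the plan bears on this point and no arithmetic applies. The check is to take each kind of change in a pre-existing condition and apply both rules.

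| Change in a pre-existing condition | Identification of Adverse Events | Pre-existing conditions sentence | Agree? |
|---|---|---|---|
| None (stable) | Not an adverse event: neither new nor an exacerbation | Not reported as one | Yes |
| Worse, but not substantially | Adverse event | Not reported as one | No |
| Substantially worse, attributed to natural history | Adverse event | Not reported as one | No |
| Substantially worse, not attributed to natural history | Adverse event | Reported as one | Yes |

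Of the three kinds of worsening, two get opposite answers.

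**What follows for an event in the two conflicting rows.** The relationship rating (Adverse Events Reporting and Evaluation; Relationship of Adverse Events to the Study Device), the seriousness assessment (Serious Adverse Events) and the severity grade (Severity) are each prescribed for adverse events. If the pre-existing-condition sentence decides what is treated as one, an event in these rows reaches none of the three. This step is an inference from how the sections fit together; the protocol does not say so outright.

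**Does a size threshold fit the rest of the section?** No. The Severity scale has a mild grade for discomfort that does not disrupt daily activity, so minor events are meant to be captured and graded.

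**Is there another place for natural history?** Yes. The relationship scale includes Unlikely Related and Unrelated. A worsening judged to be natural course can be recorded and rated there, and the judgement then stays visible and open to review.

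**Can eligible participants have such complaints?** Exclusion Criteria removes people with severe or frequent headaches, which leaves those with milder or occasional ones. Fatigue and insomnia are not named as exclusions. Dizziness is partly limited, because conditions that compromise ambulation or balance are excluded. Headache is therefore the clearest case: a modest rise in mild headaches during Study Weeks 1 to 4 is an adverse event under the definition and is not reported as one under the later sentence.

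**The case against.** **The sentence limits onward reporting only.** Adverse Events Reporting and Evaluation separates recording on the form from reporting to the sponsor or IRB, and the later sentence speaks only of reporting. On that reading every exacerbation would still be recorded and rated. This is a fair reading, and it is why one cannot state as fact that these events leave no trace on the form. It does not remove the conflict, because the same section requires all adverse events to be reported as well as recorded.

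**The sentence only explains what an exacerbation is, or keeps stable conditions off the form.** Keeping stable conditions off would need only a condition that they have worsened. The two added conditions go further and exclude real worsening, and nothing presents them as a gloss on the definition.

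**Other safeguards remain.** Substantial worsening not attributed to natural history is still reported, and the definition of unanticipated adverse device effects covers serious problems. This stands, and it confines the gap mainly to non-serious complaints.

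**The Data and Safety Monitoring Plan may settle it.** The protocol refers to that plan, but it is not among the documents. It may name an assessor or define the threshold. The protocol's own sections would still need to agree.

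A reader might also infer three stronger points that the documents do not support.

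- *That a recurrent seizure could be dismissed as natural history.* Exclusion Criteria admits someone with a seizure in the first month after stroke, but a further seizure in the trial fits the definition's new medical problem, and the same criterion treats a second seizure as a different matter. The seizure risk is described for TMS, including repetitive TMS; it is not in the list of tDCS effects. TMS is scheduled at baseline and Study Weeks 5 and 8, not during treatment.
- *That a planned safety comparison is biased.* Data Analysis plans no between-arm test of adverse events, the rule applies alike to both arms, and nothing shows that it would filter them differently.
- *That the loss can be expressed as a change in an upper confidence bound on an event rate.* Any count of filtered events would be invented, and 44 per arm is a completer target (up to 100 enrolled, dropouts replaced), not the number exposed.

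**Conclusion.** The contradiction is on the face of the text and should be corrected. Non-substantial worsening, and worsening attributed to natural history, are adverse events under the definition but are not reported as such under the later sentence. Read as written, that sentence can remove them before relationship, seriousness and severity are assessed.

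The consequence is possible under-capture of non-serious complaints that are also listed tDCS effects, with headache the clearest example. Its size cannot be estimated from the documents, and it does not touch the efficacy analyses. The finding that the passages conflict rests on the wording alone. The finding that events may go unrated also assumes that the sentence governs what is treated as an adverse event, and that no document outside those provided overrides it.

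**What to change.** Reconcile the three sections by replacing the pre-existing-condition sentence with text to this effect:

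- pre-existing conditions are noted at baseline, with their usual severity and frequency;
- a condition that stays stable is not an adverse event;
- any worsening from baseline in severity or frequency is recorded on the adverse event form, as the definition already requires;
- attribution to natural history is entered only in the study physician's relationship rating, as Unlikely Related or Unrelated where that is the judgement.

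Defining the threshold and naming the assessor would make the present sentence clearer, but would leave it at odds with the definition. A statement that form recording is unaffected would protect the record, but would leave the conflict with the rule that all adverse events are reported.

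The cost is a short protocol amendment and somewhat more forms for non-serious worsening in both arms. Medical history is already collected (Data Handling and Recordkeeping), so the baseline note adds little: usual severity and frequency, at least for the complaints listed under Device Risks. No intervention, schedule or eligibility rule changes.

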In a pilot study investigating pairing locomotor training with transcranial direct current stimulation in patients with chronic stroke²³, our research collaborator at the University of Kentucky, [name], conducted a double-blind, randomized trial of active and sham tDCS (20 min at 2mA anodal stimulation over motor cortex) delivered just prior to locomotor training using a robotic gait orthosis treadmill. Eight participants (4 men, mean age=67.8; range=44-80) with chronic left hemisphere stroke (mean years post-stroke=4; range=1.1-11.6) were tested. Performance on a 10-meter walk test was the primary outcome measure, and assessments of functional ambulation category (FAC), timed up and go, balance, and the 16 item Stroke Impact Scale (SIS 16) were secondary measures. Improvement on the 10-meter walk test and the SIS 16 following active tDCS are shown in the figure - right. Active tDCS lead to greater improvement than sham tDCS on the FAC ($p=0.028$) and similar trends were evident for the SIS 16 ($p=0.062$) and the timed up and go test ($p=0.066$). This study shows that active tDCS augments gait training and function. The data were also used for power calculations.

Hypothesis and Specific Aims

Hypothesis: Increasing cortical excitability with active anodal tDCS prior to gait training will augment recover from a stroke.

Specific Aims:

1. Determine if active tDCS augments gait. Gait speed is a primary outcome measure. Spatiotemporal and kinematic gait assessment are secondary measures of gait. Over ground laboratory assessments of gait will measure 1) gait velocity and spatiotemporal gait measures using the GAITRite electronic walkway 2) ankle, knee, and hip angles using the SIMI motion analysis system. Changes in gait parameters will be expressed as difference scores from baseline. Difference scores will be compared between the active and sham groups to determine if tDCS augments gait parameters.

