2. Determine if active tDCS augments cortical excitability after gait training. Cortical excitability will be defined by a cortical recruitment curve, a primary outcome measure, derived from plots of motor evoked potentials (MEPs) recorded from the ipsilesional TA muscle. MEPs are elicited by single pulse transcranial magnetic stimulation (TMS) delivered at increasing intensity over motor cortex. Changes in the slope of the recruitment curve signal change in cortical excitability. Difference scores from baseline will be compared between active and sham groups to determine if tDCS augments cortical excitability after FESAGT. A repeat fMRI will be performed to assess change in cortical excitability after gait training.
3. Determine if active tDCS augments physical function and social wellbeing. The Stroke Impact Scale-16 (SIS-16), a primary outcome measure, will be used to assess ADL/IADL, mobility, and social and occupational engagement at baseline and post treatment assessments. Difference scores from baseline will be compared between active and sham groups to determine if tDCS augments physical function and social well-being.

Exploratory Aim

Identify patient characteristics that predict response to treatment. Patients will be classified empirically based on their response to treatments. Regression analyses will examine whether and how initial impairment, functional level, and cortical excitability predict a treatment response.

Study Interventions

tDCS and gait training will be conducted at UCA three times a week for 4 consecutive weeks

Version 10 Revised 11/21/2014

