Power analysis: We aim to determine whether tDCS can augment the beneficial effect of gait training. Our preliminary study using tDCS to improve gait velocity and the SIS16 score yielded very large effect sizes for walking speed (2.95) and the SIS16 (1.32). In real terms, patients who received active tDCS reduced their time to walk 10 meters by about one minute (this could shave 5 minutes off a task, like getting mail, so it is functionally significant); whereas those who received sham reduced their time by only 10 seconds. Power calculations indicate that sample sizes = 11 will yield power of .95 and .80, respectively, to detect a tDCS-induced improvement gait velocity and physical function. However, assuming a very large effect size of greater than 2 is likely unrealistic. Therefore, we based our power analysis on determining a substantial meaningful change in gait speed (0.1 m/s) as determined by Perera et al.⁴⁸ Using a 2 x 3 mixed MANOVA with interaction and an estimated effect size of (Cohen's $d =$

Version 10 Revised 11/21/2014

0.39)³⁷, a conservative $r = 0.60$ ⁴⁹ and an alpha of 0.05 we will need 37 subjects per group to achieve a power of 85%. Therefore, we set our sample size at 88, so our study has sufficient power to detect meaningful changes in gait speed for individuals with chronic stroke.

We set our primary study sample size at 88, so our study has sufficient power to detect a benefit of gait training and to determine if tDCS augments improvement.

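### Aims 1-3 compare change from baseline with no baseline covariate: the test is valid, but adding one would usually make it more precise at almost no cost

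*Combined protocol and SAP*

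**What the plan says.** All three aims are analysed on change from baseline. The Data Analysis section (Aims 1-3) says "Difference scores from baseline will be calculated for each outcome measure". The Specific Aims agree: for gait, "Changes in gait parameters will be expressed as difference scores from baseline"; for the recruitment curve, "Difference scores from baseline will be compared between active and sham groups to determine if tDCS augments cortical excitability after FESAGT"; for the SIS-16, "Difference scores from baseline will be compared between active and sham groups to determine if tDCS augments physical function and social well-being".

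The model is a mixed ANOVA with group between subjects and "time of assessment (pre, weeks 1-4, & one week and one month post) as the within subjects factor". Benefit is read from "A significant group effect, with active tDCS > sham tDCS, for any of the outcome measures". The time effect is followed up with "planned contrasts where we expect post treatment assessments to be improved relative to baseline".

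No covariate is named. The Study Schedule shows gait, recruitment curve and SIS-16 all measured at baseline, but baseline values enter a model only in the Exploratory Aim, as predictors of response.

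**The concern.** Subtracting baseline fixes its coefficient at 1. Adjusting for baseline estimates the coefficient from the data, so before the small cost of that estimation it can never be less precise. When baseline and follow-up are only moderately correlated, subtraction carries baseline noise into the outcome, and the same 88 patients give a wider interval for the group difference than they need to.

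A second, smaller point lies in the time factor. It includes 'pre', where a change score is zero for every participant by construction. That level carries no information about treatment, and an average over all listed visits would include it.

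**Working it through.** **The plan's own figures.** The plan states no precision for this comparison, so there is nothing to reproduce directly. Its 37 per group (Power analysis) belongs to a 2 x 3 interaction test with d = 0.39 and r = 0.60. Of the variants tried, it was recovered only by treating 0.39 as Cohen's f with noncentrality f² x N. This gives power 0.853 with ANOVA degrees of freedom and 0.845 with MANOVA degrees of freedom at 37 per group, and r then plays no part. The scale of 0.39 is therefore open, and no power figure is built on it here.

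**Inputs from the documents.** There are 44 per arm, 88 in total (Study Population). Gait has k = 6 post-baseline visits (weeks 1-4, one week, one month). The recruitment curve has k = 2 (Protocol Summary). The SIS-16 has 2 or 6, depending on whether the schedule table or the visit text is followed, so both are shown.

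**Assumed, because the documents do not give them.** These are the ratio s of follow-up SD to baseline SD (baseline SD = 1), the baseline-to-follow-up correlation r, and the correlation ρ among follow-up visits. The value r = 0.60 is borrowed from the power statement, which does not define its role.

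**Formulas,** per patient, for the mean of k post-baseline visits, with M = s²(1 + (k-1)ρ)/k:
- change score: M + 1 - 2sr
- baseline-adjusted: M - (sr)²
- difference: (1 - sr)², never negative, and zero only at s = 1/r

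Estimating the slope multiplies the adjusted variance by about 1 + 1/84 = 1.012.

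**Equal SDs (s = 1):**

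| r | ρ | k | Change | Adjusted | Cut | Cut after slope cost |
|---|---|---|---|---|---|---|
| 0.60 | 0.60 | 2 | 0.600 | 0.440 | 27% | 25.8% |
| 0.60 | 0.60 | 6 | 0.467 | 0.307 | 34% | 33.5% |
| 0.60 | 0.90 | 2 | 0.750 | 0.590 | 21% | 20.4% |
| 0.60 | 0.90 | 6 | 0.717 | 0.557 | 22% | 21.4% |
| 0.80 | 0.80 | 2 | 0.300 | 0.260 | 13% | 12.3% |
| 0.80 | 0.80 | 6 | 0.233 | 0.193 | 17% | 16.2% |
| 0.90 | 0.90 | 2 | 0.150 | 0.140 | 7% | 5.6% |
| 0.90 | 0.90 | 6 | 0.117 | 0.107 | 9% | 7.5% |

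Example, row 3: M = (1 + 0.9)/2 = 0.95; change 0.95 + 1 - 1.2 = 0.75; adjusted 0.95 - 0.36 = 0.59; cut 0.16/0.75 = 21%.

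**Unequal SDs, ρ = r (k = 2, then k = 6):**
- r = 0.60, s = 1.2: 0.712 vs 0.634 (11%); 0.520 vs 0.442 (15%).
- r = 0.60, s = 0.8: 0.552 vs 0.282 (49%); 0.467 vs 0.196 (58%).
- r = 0.80, s = 1.2: 0.376 vs 0.374 (0.4%); 0.280 vs 0.278 (0.6%). After the slope cost these become net losses of about 0.8% and 0.6%.
- r = 0.90, s = 1.11 (where sr is about 1): a net loss of about 1.2%, which is the slope cost itself.

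**Validity.** In simulations under no effect (44 per arm, 8,000 trials per setting, r = 0.6 and 0.9, k = 2 and 6), the mean change-score difference lay between -0.0001 and 0.0004. Type I error was 0.046 to 0.057, with no consistent inflation.

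**The 'pre' level.** With a zero added for everyone, each patient's mean over k + 1 levels is k/(k+1) of the post-baseline mean. The estimate and its standard error shrink by the same factor, so the group test statistic is unchanged. A reported all-visit mean difference would be 6/7 of the post-baseline difference for gait and 2/3 for the recruitment curve.

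**The case against.** The strongest reply is that this is a preference for efficiency, not an error. That stands, and the point is put only as a free improvement.

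The size is also uncertain. The plan calls 0.60 conservative and cites a reliability study of gait tests for it. If the true correlation is higher, the gain moves towards the 7-9% end. The 34% figure further needs follow-up visits to correlate no better with each other than with baseline; with ρ = 0.9 the six-visit gain falls to 22%. Both objections stand and are built into the range.

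Four stronger readings are tempting, and the documents do not support them:
- *The change-score test is biased or invalid.* Randomisation makes it unbiased, and the simulations agree.
- *The trial loses a stated amount of power.* Converting variance into power needs an effect in known units, and the scale of 0.39 is not given. The power statement also concerns an interaction, not the group effect tested here.
- *Including 'pre' weakens the group test.* In the planned ANOVA it does not. The dilution matters only if an all-visit mean is reported, and none is explicitly planned.
- *The ANOVA is really of raw scores.* Listing 'pre' and contrasting with baseline would fit that, and the group main effect would then be a different test. But the Data Analysis section and all three aims specify difference scores.

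**Conclusion.** The point holds as a free improvement. The planned comparison is valid but generally less precise than the same data allow. With equal SDs the variance saving is about 21-34% if baseline and follow-up correlate at 0.60. It is 13-17% at 0.8 and 7-9% at 0.9 when all visits share one correlation. These are illustrations: the documents give no SDs, no correlation among follow-up visits, and no correlation for the recruitment curve or SIS-16. The downside is bounded by the slope cost, about 1.2% of variance, so in the least favourable case (follow-up SDs above baseline SDs with high r) the result is nil or a loss of about 1%. No gain in power is claimed. The 'pre' level is a wording fault that leaves the group test intact.

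**What to change.** Keep difference scores and the planned Aims 1-3 model, with these changes:

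- Add the baseline value of the same measure, centred at its overall mean, as a covariate.
- Remove 'pre' from the time factor, leaving only post-baseline visits. The group test does not change, and any reported all-visit mean difference is no longer diluted by baseline zeros.
- State that the treatment test is the group difference over the post-baseline visits.
- Restate the planned contrast against baseline as a test of mean change against zero.

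Suggested wording: *Change from baseline at the post-baseline visits will be analysed with group, visit and their interaction, adjusting for the centred baseline value of the same measure. Baseline is not a level of visit. The treatment test is the group difference over the post-baseline visits; improvement over time is tested as mean change against zero.*

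A linear mixed model of post-baseline values with baseline as covariate is an acceptable equivalent. Moving baseline to the other side of the equation only raises its coefficient by 1 and leaves the group estimate the same.

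Cost: one degree of freedom and a wording change, with no new data or visits.
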